On this day, prior to socket fitting activities, the arterial blood flow will be measured on the index stump if not already completed per standard of care within the previous 12 months prior to enrollment for data analysis. Those with an TcOM < 30 mmHG be excluded and no further study activities will be completed. These subjects will be recorded as a screen fail and will not be enrolled.

Others will move forward with socket fitting activities.

- A. **Study Visit #1 - Socket Fitting visits (Week 0 - 4, +/- 2 weeks) – Note: this visit may consist of three (minimum) visits plus socket adjustment visits (as needed by the subject) on separate days (up to 4 weeks)**
 - i) limb shape capture, measurements or tracing
 - ii) diagnostic static fitting and diagnostic dynamic fitting
 - iii) delivery of definitive “research” socket

Once delivery of the definitive research socket has been completed, the subject will be allowed to return for no greater than 4 adjustments (within 0-2 weeks from baseline) to obtain a comfortable fit in order to complete this study. If subject requires more than 4 adjustment visits, the participation from the study will end.

Once the subject is comfortable with the fitting, the date will be noted by the study team as **“research socket use start date”**. From this date, the subject will begin wearing the test socket for next 16 weeks.

- B. **Study Visit #2A - Baseline visit for residual limb health (Week 4, +/- 2 weeks)** Enrollment, after delivery of the definitive research socket and completion of the socket fitting visits, the following research activities will take place to obtain baseline measurements:

- Subjects will be asked to walk on a treadmill for 10 mins. The residual and sound (intact) limb health measurements will be taken before and after the activity period with the exception of conducting post-activity ultrasound and digital imaging. The purpose of acquiring ultrasound and digital imaging is to determine changes in skin structure on a long-term basis; thus, these measurements will only be collected during pre-activity procedures to observe changes in a resting state. The following health measurements will take place:
 - Surface Electrical Capacitance
 - TEWL measurement
 - Hyperspectral Imaging
 - Ultrasound (pre-activity only)
 - Perfusion/ Blood flow
 - Digital Image (pre-activity only)

B.i. Study Visit #2B - Baseline visit for gait assessment (Week 4, +/- 2 weeks)**

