***Note* Study Visit #2A and #2B can be combined and performed in a single study visit upon the discretion of the subject.**

Subjects will begin in their current standard of care prosthesis (the prosthesis worn at time of study enrollment), wherein the following research activities will take place in the following order:

- Subjective questionnaires [Veterans RAND 36-Item Health Survey (VR
- 36, PEQ, Socket Comfort Scores (SCS), and National Institute of Health (NIH) Patient-Reported
- Outcomes Measurement Information System (PROMIS)
- Functional evaluation [Comprehensive High-level Activity Mobility Predictor (CHAMP)]
- Biomechanical evaluation of gait during 6min walking test
 - a. Positioning markers will be placed on the subject while performing the walking assessment to track and describe the movement of the body in three dimensions.
- Repeat SCS outcome

**** applicable to any new enrollments and/or any already enrolled subject completed their limb health part (16 weeks in test sockets followed by 4 weeks in SoC socket as wash off period)**

Following completion of these activities in study visit 2A & B, the subjects will be fitted with the adaptive vacuum suspension by a certified prosthetist that they will wear subsequently wear the device for 16 weeks

The study team will follow up subjects with a weekly phone call to determine the compliance for the use of research socket.

C. **Study Visit #3A – Final Visit (Week 16, +/-2 weeks).** After 16 weeks of wearing the “research” socket the following research activities will take place in the following order:

- Subjects will be asked to walk on a treadmill for 10 mins. The following residual and sound limb health measurements will be taken before and after the activity period with the exception of conducting post-activity ultrasound and digital imaging, is as follows
 - Surface Electrical Capacitance
 - TEWL measurement
 - Hyperspectral Imaging
 - Ultrasound (pre-activity only)
 - Perfusion/ Blood flow
 - Digital Image (pre-activity only)

C.i **Study Visit #3B**— the visit will take place either the same day of Visit 3A or another day within the Week 16, +/-2 weeks based on subject convenience, to repeat research activities previously performed in study visit # 2A

- Subjective questionnaires [Veterans RAND 36-Item Health Survey (VR 36, PEQ, Socket Comfort Scores (SCS), and National Institute of Health (NIH) Patient-Reported Outcomes Measurement Information System (PROMIS)]

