Patients will be informed during the informed consent process (in writing and verbally) that they are free to withdraw from the trial at any time. The Investigator may exercise his medical judgment to terminate a patient's participation in the trial due to clinically relevant changes in any clinical or laboratory parameter. The Sponsor-Investigator also reserves the right to discontinue/terminate the trial at any time.

Discontinuation criteria for individual subjects include: (1) Non-compliance with the inclusion/exclusion criteria, (2) treatment non-compliance, such as use of another socket, (3) withdrawal from the study due to reasons not related to the treatment.

XIII. Procedures for Amendment of Protocol:

Protocol modifications will be approved by the IU IRB prior to implementation and WRNMMC site HQ will be notified if the change is significant or adversely impacts the risk/benefit assessment for the study.

As per IU HRPP guidance on NSR devices reviews trial monitoring, an internal review of data/source verification will be performed and documented on a quarterly basis. The internal reviewer will conduct the following activities: quarterly observation of research recruitment, informed consent process, research activities completed at research study visits, data collection and analysis. The internal review process may meet more frequently as deemed necessary and will be immediately notified of any serious and/or unanticipated event(s) related to procedures of the study. They will review all summary data, overall progress of the study and any individual serious and/or unanticipated event report(s). They do not have any conflicts of interest with the study team and/or protocol. In addition, a Data Safety Monitoring Board (DSMB) will provide independent oversight of the study, and will meet with the PI and research team at the following intervals: (1) prior to enrollment, after enrollment of the first 15 subjects for Aim 2, after enrollment of the first 30 subjects for Aim 3, and after all subjects have been enrolled and within 60 days of completion of the study for both Aims 2 and 3. The DSMB will consist of a physician chairperson, a statistician, and a clinical trialist/ethicist. The Data Safety Monitoring Board will meet at the same intervals separate of the internal research reviewer. .

XIV. Payment:

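### Aim 3 removes subjects who need a fifth adjustment or use another socket and plans no Week 16 outcome or count for them, so the comparison probably leans towards the test socket

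*Combined protocol and SAP*

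**What the plan says.** Section VIII, Study Visit #1, allows up to four adjustments after the definitive socket is delivered, "to obtain a comfortable fit in order to complete this study". It then states: "If subject requires more than 4 adjustment visits, the participation from the study will end". The 16-week wear period has its own gate: "Once the subject is comfortable with the fitting, the date will be noted by the study team as" the start date for research socket use.

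Section XII lists "treatment non-compliance, such as use of another socket" among the discontinuation criteria for individual subjects. Section VIII also provides weekly telephone calls about compliance, so socket switching should come to light.

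The comparator at Visit 2B is the prosthesis the subject already wore at enrolment. No adjustment limit or switching rule applies to it.

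Section VIII gives two orders for fitting and baseline. Visit 2A takes place "after delivery of the definitive research socket and completion of the socket fitting visits". The text after Visit 2B says: "Following completion of these activities in study visit 2A & B, the subjects will be fitted with the adaptive vacuum suspension".

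Section XV specifies a random-effects linear regression and a Holm adjustment at 0.05 overall. It names no analysis population, missing-data method or sensitivity analysis, and does not plan to report fitting failures or socket switches.

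**The concern.** Both rules end participation in the study, not only use of the research socket, and both act on one side of the comparison. A subject who cannot be made comfortable in the test socket leaves. A subject who is uncomfortable in the standard-of-care prosthesis does not. If those removed would have done worse than average in the test socket, the Week 16 mean among those who remain is too good.

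The concern is sharpest for the Socket Comfort Score, which is collected at Visits 2B and 3B: the gate selects on almost the same thing that the score measures. For CHAMP and limb health, a positive link between tolerance and outcome is plausible but not shown.

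Aim 3 sets out to compare the effectiveness of the adaptive vacuum system with standard of care. A reader of that result would want to know how many subjects could not use the system, and as written the plan would not say.

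**Working it through.** **What the documents allow.** They give no power calculation, SD, effect size or expected removal rate, so there is no planned figure to reproduce. The check has two parts: where removed subjects sit in the data, and an illustration under stated assumptions.

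**1. Position in the data.**
- *Fifth adjustment, fitting before Visit 2A.* The subject leaves before baseline and contributes no rows. A random-effects model cannot recover them.
- *Fifth adjustment, fitting after Visits 2A and 2B.* The subject has a baseline but no Week 16 value.
- *Use of another socket during the 16 weeks.* The subject has a baseline but no Week 16 value. The model can use the baseline, but is valid only if missingness is at random given the observed data. That is doubtful where the switch came from rejecting the device.

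The selection arises under either timing.

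**2. Illustration.** Assumptions, none from the documents:
- The paired change, in SD units, is normal with true mean 0 and variance 1 among all enrolled.
- The fraction d with the lowest tolerance is removed.
- Tolerance correlates ρ with the change.
- The test is a single two-sided paired test at 0.05, without Holm.

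Formulas, with z_d the d-quantile of the standard normal, φ its density, N the number enrolled and n = N(1 − d), rounded:
- m = φ(z_d)/(1 − d)
- completer mean = ρm
- completer variance v = 1 − ρ²m(m − z_d)
- SE = √(v/n)
- rejection probability = 1 − Φ(1.96 − ρm/SE) + Φ(−1.96 − ρm/SE)

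Worked case, N = 60, d = 0.10, ρ = 0.5: z_d = −1.282, φ = 0.1755 and m = 0.1755/0.90 = 0.195. The shift is 0.5 × 0.195 = 0.097. The variance is v = 1 − 0.25 × 0.195 × 1.477 = 0.928, so with n = 54, SE = √(0.928/54) = 0.131. The ratio is 0.74 and the rejection probability 0.115.

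| Enrolled | Removed | ρ | Shift (SD) | False positives |
|---|---|---|---|---|
| 60 | any | 0 | 0 | 5% |
| 60 | 5% | 0.5 | +0.05 | 7% |
| 60 | 10% | 0.5 | +0.10 | 12% |
| 60 | 15% | 0.3 | +0.08 | 9% |
| 60 | 15% | 0.5 | +0.14 | 18% |
| 60 | 20% | 0.5 | +0.18 | 25% |
| 30 | 10% | 0.5 | +0.10 | 8% |
| 30 | 20% | 0.5 | +0.18 | 15% |

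A simulation of 1,000,000 draws at ρ = 0.5 gave completer means of 0.098 (10% removed) and 0.176 (20% removed), matching the formula.

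**Multiplicity.** Section XV does not give the number of tests. If the strictest Holm step were 0.05/4, the 18% in the table would fall to about 7%, against a nominal 1.25%.

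**Direction.** At ρ = −0.3 with 20% removed, the shift is −0.11 SD. The bias reverses if those removed would have done better than average in the test socket.

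**The case against.** The strongest reply is that the fitting rule works as a run-in. If it acts before baseline and before the research socket start date, those subjects never enter the paired contrast, and the result describes successfully fitted users. That is a legitimate question for a device, and this much stands. But the plan does not declare that population, and Aim 3 is worded as effectiveness against standard of care.

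Several stronger readings are tempting and go beyond the text:
- *The effect is biased in favour of the device.* A reader might infer this as fact. The documents give no removal rate and no link between tolerance and outcome, and with no correlation there is no bias.
- *Week 16 holds only those who tolerated the device.* Subjects who dislike the socket but keep wearing it remain.
- *Both rules are triggered by rejection of the test system.* Section XII gives no reason for using another socket; breakage, travel or convenience would count too. A fifth adjustment may reflect limb-volume change or the fitting itself rather than the vacuum suspension.
- *Fitting failures certainly have no data at all.* Section VIII contradicts itself on the order of fitting and baseline.
- *The problem covers all 120 Aim 3 subjects.* The rules are shown in the Indiana University protocol. Section V says OWW and WRNMMC have separate protocols. The WRNMMC protocol, covering 60 subjects, is not shown.

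It is also fair to object that Visit 3 alone gives no change score to a subject without a Visit 2. A removed subject assessed in the original prosthesis also says little about limb health under vacuum. The fix has to allow for both.

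**Conclusion.** The point holds in a limited form. Under the Aim 3 rules shown here, stated criteria remove subjects according to how they fare with the test socket only, and nothing is planned to measure or count those removed. A lean towards the test socket is the expected direction, with the firmest case for the Socket Comfort Score and a weaker one for CHAMP and limb health.

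The size cannot be derived from the documents. In the illustration it runs from nothing, through about +0.08 SD and 9% false positives (15% removed, correlation 0.3), to about +0.18 SD and 25% (20% removed, correlation 0.5). These figures rest on a true null, 60 enrolled, normality and an unadjusted 0.05. Holm adjustment or 30 enrolled lowers the false-positive rates, but neither removes the shift in the mean. The change is worth making because it is cheap and because, without it, a reader could not judge how far the result depends on exclusions.

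**What to change.** Leave the rules for ending socket use as they are.

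1. **Sections VIII and XII.** Separate stopping the research socket from leaving follow-up. Invite removed subjects who have a baseline to Visits 3A and 3B at the same calendar time, in whichever prosthesis they then use, and record which it is.
2. **Section VIII.** Reconcile the two statements on whether fitting comes before or after Visits 2A and 2B. Visit 2B is done in the subject's own prosthesis, so taking that assessment before fitting would give fitting failures a baseline.
3. **Section XV.**
   - Analyse all who started fitting, where data exist.
   - Report the proportions of fitting failures and socket switches with an exact confidence interval and the reasons.
   - Add a worst-rank sensitivity analysis that gives failures due to poor fit or rejection the lowest rank.
   - Label the completer analysis as applying to successfully fitted users only.

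The failure count and the worst-rank analysis need no extra visits, so they work even if no removed subject returns.

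The cost is wording in three sections, a few retained Visit 3 assessments, and possibly a change to section XIV, which withholds payment when study visits are not completed. The estimate may become somewhat less favourable to the test socket.

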Achieving a comfortable and functional connection between an amputee and their prosthetic limb is critical to the success of the prosthesis. Therefore, the socket system is the most significant component for overall success of the prosthesis^{1,2}. In an effort to maximize socket performance and comfort without adversely affecting residual limb health, a prosthetist custom fits a socket for every patient using plaster wraps or computer aided design. Currently, this process suffers from a lack of quantitative feedback to determine appropriate socket fit. Prosthetists aim to minimize suspension-dependent movement between the socket and residual limb, but current approaches are limited as they rely on anecdotal visual cues along with subjective verbal feedback from the patient. Prosthetists then use this information to revise socket parameters such as volume, geometry, and type of suspension to provide current 'best' fit for a patient. Regardless of prosthetist fitting, the volume of mature residual limb (>18 months post-amputation³) are subject to daily⁴ and chronic^{5,6} changes in volume that compromise socket fit and performance. For the 1 million Americans that live with a lower-limb amputation, a growing number of which are service men and women⁷⁻⁹, these volume changes adversely affect fit, performance, and residual limb health⁶ – including skin breakdown and ulceration¹⁰ that can necessitate revision of the amputation. Indeed, for traumatic lower-limb amputations, the requirement for surgical revision is known to be as high as 30%¹¹.

II. Objective:

Aim 1 will evaluate the relationship between vacuum pressure and limb movement inside the socket and how it changes with respect to vacuum pressure setting, gait speed and socket volume

Aim 2 will evaluate the impact of socket movement on residual limb circulation and residual limb skin health

Aim 3 will compare the effectiveness of an adaptive vacuum system to standard of care suspension prosthetics (pin-locking or suction).

Study Population: Up to 170 amputees will be enrolled in the study overall.

1. **Aim 1:** 10 trans-femoral amputees and 10 trans-tibial amputees will be enrolled.
2. **Aim 2:** 15 trans-tibial and 15 trans-femoral amputees will be enrolled.
3. **Aim 3:** n=120 (trans-tibial and trans-femoral amputees) will be enrolled.

III. Inclusion Criteria:

1. Ages of 18 and above

2. Unilateral trans-tibial or trans-femoral amputee
3. Ambulate at a K2 level or higher

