All subjects will be compensated \$100 for each of the completed visits. Aim 1 subjects will be compensated \$100 for the completed study visit 1. Aim 2 subjects will have 4 total visits and will be eligible for a maximum of \$400 for completion of all study visits. Aim 3 subjects will have 3 total visits and will be eligible for a maximum of \$450 for the completion of all visits per following schedule: Visit #1 (\$50), Visit #2A & B (\$150, for completing all socket fitting activities

& baseline) and Visit #3A&B (\$250). Subjects will not be paid if any of study visits are not completed.

XV. Statistical Analysis:

Patient demographics and clinical characteristics will be described using frequencies and percentages for categorical data and median and the interquartile range (IQR) for continuous data. In Aim 1, random-effects linear regression will be used to assess the relationship between wave amplitude and distal movement (or lateral shift) controlling for vacuum pressure. Patient ID will be the random-term in the model. In Aim 2, random-effects linear regression will also be used to compare percent change in limb perfusion across adaptive EVS and suction at 12 weeks controlling vacuum pressure and controlling for the baseline EVS and suction values. In Aim 3, a random-effects linear regression model will be used to establish the relationship in amputee performance (as measured by the CHAMP tasks) and residual limb health across EVS and suction and across EVS and pin-locking/lanyard in a cross-over design. The model includes terms for group (EVS vs. suction or EVS vs. pin-locking/lanyard), sequence (EVS to suction vs. suction to EVS or EVS to pin-locking/lanyard vs. pin-locking/lanyard to EVS), and visit (second vs. first). All statistical models will account for the effect of age, diabetes status and smoking history by including them as the covariates in the models. As per need, subjects may be stratified based upon diabetes status and arterial blood flow status. The *p*-values produced in the study will be adjusted using the Holms procedure to control the overall type I error at 0.05 due to the multiple comparisons. All analyses will be run using Stata 13.1, Stata Corporation, College Station, Texas.

XVI. References:

1. Lake, C. The evolution of upper limb prosthetic socket design. *Journal of Prosthetics and Orthotics* 20, 85 (2008).

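### In the IU Aim 3 schedule the 16 weeks of research-socket wear has two start points, so the limb-health baseline (Visit 2A) may follow some wear of the device

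*Combined protocol and SAP*

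**What the plan says.** Section II states that Aim 3 will "compare the effectiveness of an adaptive vacuum system to standard of care suspension prosthetics". Section VIII gives the IU schedule (n=30).

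- **A, Study Visit #1 (fitting).** After delivery of the definitive socket up to 4 adjustments are allowed. When the subject is comfortable, the team records a research-socket start date: "From this date, the subject will begin wearing the test socket for next 16 weeks".
- **B, Study Visit #2A.** This is the "Baseline visit for residual limb health (Week 4, +/- 2 weeks"), held "after delivery of the definitive research socket and completion of the socket fitting visits". It includes a 10-minute treadmill walk with capacitance, TEWL, hyperspectral imaging, ultrasound and perfusion. No socket is named.
- **B.i, Study Visit #2B (gait and questionnaires).** Here the socket is named: "Subjects will begin in their current standard of care prosthesis (the prosthesis worn at time of study enrollment"). 2A and 2B may be combined, but need not be.
- **Text closing Visit 2B.** "Following completion of these activities in study visit 2A & B, the subjects will be fitted with the adaptive vacuum suspension", which is then worn for 16 weeks.
- **C, Study Visit #3A.** The limb-health set is repeated at the "Final Visit (Week 16, +/-2 weeks"), after 16 weeks of wear.

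Section V gives a third order, with baseline at week 0 and fitting over weeks 0 to 4. Section XV models CHAMP performance and "residual limb health across EVS and suction and across EVS and pin-locking/lanyard in a cross-over design". EVS is the plan's abbreviation for the vacuum suspension.

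**The concern.** The same 16-week period is started twice: on or before Visit 2A under Study Visit #1, and after 2A and 2B under Study Visit #2B. A site that follows the first instruction can send the subject home in the research socket and take the limb-health baseline later. The baseline then already carries some device exposure.

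The difference between 3A and 2A would then describe how limb health changes between an early and a late point of vacuum wear, which is not the comparison Aim 3 sets out to make. A null result could not be told apart from a baseline already shifted by the device. Adjusting for age, diabetes and smoking, as Section XV plans, would not correct this.

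**Working it through.** The plan gives no figure to reproduce here. The check compares the order of events and then subtracts visit windows.

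**Step 1: order of events**

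| Section VIII location | Start of the 16 weeks | Position of 2A |
|---|---|---|
| A, Study Visit #1, with the 2A text | Recorded date, when the fit is comfortable | After delivery and completed fitting, so on or after the start |
| Text closing Study Visit #2B | After 2A and 2B are completed | Before the start |

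The two agree if 2A and 2B are both held on the recorded date, before the socket goes home. Nothing requires that. Treating the test socket and the vacuum suspension as separate steps does not help, because both carry the 16-week wear period.

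Two other passages bear on the order.
- The double-asterisk note under Visit 2B covers enrolled subjects who finished 16 weeks in the test socket, plus 4 weeks of washout, before their gait baseline. Their limb-health wear preceded 2B, so the sentence closing 2B cannot describe it. The washout came after that wear and does not protect their 2A.
- Section XII counts use of another socket as treatment non-compliance. This discourages standard-of-care wear once the start date is recorded.

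**Step 2: possible prior wear**

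Let s be the start week, b the week of 2A, and g = b − s the prior wear. Assumptions: weeks run from enrolment, and s lies between 2 and 4. The 2A window (Week 4 ± 2) gives b from 2 to 6, with b not before s.

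| s | g with 2A at Week 4 | g over the whole window |
|---|---|---|
| 2 | 4 − 2 = 2 | 0 to 6 − 2 = 4 |
| 3 | 4 − 3 = 1 | 0 to 6 − 3 = 3 |
| 4 | 4 − 4 = 0 | 0 to 6 − 4 = 2 |

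Home wear between delivery and the start date, if any, adds to g. With 3A at s + 16, the interval from 2A to 3A is (s + 16) − b = 16 − g: 16 weeks for g = 0, 14 for g = 2, 12 for g = 4.

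**Step 3: what 3A minus 2A estimates**

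Let L0 be the mean standard-of-care value and L(t) the mean after t weeks of wear. The intended contrast is L(16) − L0. With prior wear it becomes L(16) − L(g), which differs from the target by −(L(g) − L0). The documents give no time course, so neither the sign nor the size of this term is known.

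Purely as an illustration, the share of a 16-week effect already present at week g would be:
- steady build-up, g/16: 2/16 = 12.5% and 4/16 = 25%;
- assumed 2-week half-life, (1 − 2^(−g/2))/(1 − 2^(−8)): 0.5/0.9961 = 50% and 0.75/0.9961 = 75%.

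If a new socket first irritates the skin, L(g) can lie on the other side of L0 and the difference is exaggerated instead.

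**Step 4: alternative baselines**

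The instrumented set is scheduled only at 2A and 3A. Stump oxygen (TcOM) before fitting is an eligibility value that may be up to 12 months old, and no matching TcOM is named at 3A. The Residual Limb Health scale of the PEQ is collected at 2B in the standard-of-care prosthesis, but it is self-reported.

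**Step 5: the Week 16 label**

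Counted from enrolment with wear starting at Week 4, 16 weeks of wear ends at 4 + 16 = Week 20, outside the 14-to-18 window. The label fits only if weeks are recounted from the start date. This is a minor wording point, since Visit 3A is clearly meant to follow 16 weeks of wear.

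**The case against.** The strongest reply is that the order is ambiguous, not forced. Study Visit #1 allows adjustments within 0 to 2 weeks of a baseline. If that baseline is Visit 2A, adjustments and the start date can follow it, in agreement with the sentence closing Visit 2B. That sentence is also the only one that expressly orders wear against 2A and 2B. This stands as far as it goes, but the 2A text puts the visit after completed fitting and so points the other way.

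A reader might infer more than the documents support:

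- That 2A is done in the research socket or after wear. The text leaves both unspecified and does not show how visits were timed.
- That no other standard-of-care value for limb health exists. The PEQ scale at 2B is one; the point holds for the instrumented measures only.
- That the model would code 2A as standard of care. Section XV does not say how 2A enters.
- That a known fraction of the effect is lost. The shares in Step 3 rest on assumed time courses, and g = 4 needs fitting to end at Week 2 with 2A at the last allowed time.
- That subjects who fit quickly have the longest prior wear. This requires 2A to be held near calendar Week 4; if completed fitting triggers the visit, it need not follow.
- That a clean 2A removes all difficulty. New IU subjects all go from standard of care to EVS, so device and time coincide even when g = 0.

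**Conclusion.** The concern holds in a limited form. Section VIII gives two incompatible start points for one wear period and names no socket at the limb-health baseline. Followed as written under Study Visit #1, it allows about 0 to 2 weeks of prior wear when 2A is at Week 4 and fitting ends at Weeks 2 to 4. More is possible at the window limits or with home wear during adjustments. In that case 3A against 2A estimates change during EVS wear for the instrumented measures.

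The bias is possible, not demonstrated, and its size and direction are unknown. The timing rests on counting weeks from enrolment and on the assumed end of fitting. The schedule is confirmed only for the 30 IU subjects; Section V says that OWW and WRNMMC work under separate IRB protocols. It is worth fixing because it touches the only instrumented pre-treatment value and the remedy is cheap.

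**What to change.** **For subjects still to be measured**
- Hold 2A in the standard-of-care prosthesis, and say so as Visit 2B does. Take it before the research socket is put on that day and before any take-home wear: at the delivery visit at the latest, or at week 0, which Section V already lists.
- For new enrolments, complete 2B before the socket goes home.
- Keep the recorded date of comfortable fit as the single anchor for the 16 weeks, and time 3A and 3B at +16 weeks ± 2 from it. Record any wear during adjustments.
- Align Section V and the Visit 1, 2A and 2B texts of Section VIII accordingly.

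**For subjects already measured**
- Extract the socket worn at 2A and the delivery, start and 2A dates, and report the distribution of prior wear.
- Keep all subjects in the main analysis. Add a sensitivity analysis limited to those whose 2A was done in the standard-of-care prosthesis with no prior wear. Describe the others as change during EVS wear.

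**Cost**
- An amendment is needed, with no extra visit if 2A is combined with delivery. Section VIII cites a study end of 09/2021, so the amendment may reach few subjects and the retrospective step may matter more. The socket worn at 2A may have to come from source notes.
- Some baselines will come from subjects who later leave for needing more than 4 adjustments.
- The interval from baseline to final visit will exceed 16 weeks. Before the ± 2-week allowance it is up to 16 + 2 = 18 weeks from a delivery-day 2A if adjustments take up to 2 weeks, or about 16 + 4 = 20 from a week-0 2A with the start at Week 4.
- The change does not separate device from time in subjects who all go from standard of care to EVS.
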